Title: Postoperative Activity Restrictions in Children (PARC)

NCT04145895

Protocol approval date: 10/29/2021

Title: Postoperative Activity Restrictions in Children (PARC)

Principal Investigator: [name]

NCT04145895

Protocol approval date: 10/29/2021

IRB# 2019-224

SUMMARY

BACKGROUND: Currently, there are no evidence-based guidelines for postoperative activity restrictions in routine pediatric surgery. Recent studies suggest that patients may return to normal activity earlier than previously thought. We aim to compare time to full activity and post-operative outcomes. This study will describe family preferences for self-directed activity restrictions (SDAR) and physician directed activity restrictions (PDAR) following routine surgeries.

STUDY DESIGN: Single institution, prospective clinical trial (NCT04145895). Patients who present for a routine inguinal hernia repair or laparoscopic appendectomy for uncomplicated appendicitis are eligible for participation. Participating families will choose to enroll in either the control (PDAR) or experimental (SDAR) groups. The PDAR patients are restricted from full activity for two weeks post-operatively. For SDAR, patients are instructed to return to full activity when pain is improving and the family feels comfortable. At 4-6 weeks postoperatively, caregivers will complete a survey to assess time to resume full activity, time to return to school and work, surgical complications, and patient and caregiver satisfaction.

BACKGROUND AND SIGNIFICANCE

Postoperative activity restrictions (PAR) serve to minimize the risk of complications and prevent stress on the operative site following abdominal surgery. By minimizing intra-abdominal pressure, PAR are used to prevent the breakdown of the surgical repair and closure.¹ Commonly restricted activities include heavy lifting, exercise, and strenuous activity. As children are highly active by nature, limiting physical activity is difficult.² Pediatric surgeons may restrict time to return to school or extracurricular activities. However, these restrictions create a societal burden through school absences and missed work days. Additionally, PAR can negatively impact a child's psychosocial well-being and cause undue family stress.²

[figure not shown]

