This study was approved by the Beaumont Institutional Review Board (2019-224). Patients who presented to Beaumont Royal Oak and Beaumont Troy for a routine inguinal hernia repair (ages 2-13 years) or laparoscopic appendectomy for uncomplicated appendicitis (ages 0-17 years) were eligible for participation. Patients meeting eligibility criteria (**Figure 1**) were identified by the pediatric surgeons, including the Primary Investigator ([name]), and were provided with an information sheet detailing the study, which served as consent for participation. Parents and patients who elected to participate then chose to enroll in the control group (PDAR) or experimental group (SDAR). The PDAR instructions detailed that patients are restricted from full, normal activity for 2 weeks after their procedure. The SDAR instructions specified that they may return to full activity when their pain is improving and the parent, or guardian, feels comfortable advancing their activity. Enrollment is still accruing for this study.

Figure 1. Patient eligibility criteria**Figure 1.** Patient eligibility criteria for participation in the clinical trial.

Data Collection

Baseline characteristics, comorbidities, surgical complications, length of stay, and pain medications will be obtained for each participant from the time of surgery. At 4-6 weeks postoperatively, parents or guardians will be asked to complete a survey at their follow-up appointment or online using Research Electronic Data Capture (REDCap). The survey includes assessments of the time taken to return to school and work, return to full activity, surgical complications, and patient and caregiver satisfaction (**Figure 2**).

Figure 2. Postoperative Survey

Your Child's Experience Postoperatively	
For how long was your child on pain medications following the procedure?	 1-2 days  3-4 days  4-7 days  >1 week
How many days following the procedure did your child return to school, daycare, summer camp, or summer school?	
Approximately how many days after surgery did your child return to full activity (sports, gym, dance, outdoor play, etc.)?	
Did your child's wound have any oozing or bleeding following discharge from the hospital?	 None  Mild (slight drainage)  Moderate (drainage with blood)  Severe (oozing with blood)

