If you answered mild, moderate, or severe to the previous question, when did this occur?	
If you answered mild, moderate or severe to the previous question, did this require any treatment by your surgical team?	
Did your child experience any postoperative complications?	 No  Yes
If you answered yes to the previous question, please specify:	
After resuming full activity, did your child experience an increase in pain?	 No  Yes
If you answered yes to the previous question, did they require any medication for the pain?	 No  Yes
How compliant was your child with their postoperative instructions?	 Compliant  Partially compliant  Not compliant

Postoperative Activity Restrictions in Children After Routine Surgery

5

How would you describe your child's overall satisfaction following the procedure?	 Very satisfied  Satisfied  Neither satisfied or dissatisfied  Dissatisfied  Very dissatisfied
Your Experience Postoperatively	
What is your relationship to the child?	 Mother  Father  Grandparent  Legal Guardian  Other
Did you or another caregiver take time off work to care for your child following their procedure?	 Yes  No
Did you have to find additional childcare for your child following their procedure?	 Yes  No
How would you describe your overall satisfaction following your child's procedure?	 Very satisfied  Satisfied  Neither satisfied or dissatisfied  Dissatisfied  Very dissatisfied
Were you satisfied with the instructions detailed in your discharge guidelines?	 Very satisfied  Satisfied  Neither satisfied or dissatisfied  Dissatisfied  Very dissatisfied

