If your followed physician-directed instructions, did you follow the recommendations strictly?	 Yes  No  Somewhat
If you chose self-directed instructions, did you feel comfortable determining when your child was able to resume full activity?	 I felt comfortable  I had some concerns  I did not feel comfortable

Figure 2. Postoperative survey provided to patients 4-6 weeks following their procedure. Patients were able to complete the survey at their postoperative visit or online via REDCap.
	

Objectives

The primary outcome of this study is length of time to full activity.

Secondary outcomes will evaluate patient preference to PDAR and SDAR based on choice of study arm and the impact of restriction type on number of parental days off work.

Clinical complications will also be tracked. Patient satisfaction will be defined as a cumulative score of three satisfaction factors (child, parent, and satisfaction with discharge guidelines).

Statistical Analysis

Continuous data will be presented as mean (SD) or median (IQR) depending on distribution, and analyzed using unpaired t tests or Mann Whitney ranked sum tests. Categorical data will be presented as number (%) and will be analyzed using Chi Square or Fisher's exact test depending on frequencies P values <.05 will be considered significant.

REFERENCES

3. Pommergaard H-C, Burcharth J, Danielsen A, Angenete E, Haglind E, Rosenberg J. No consensus on restrictions on physical activity to prevent incisional hernias after surgery. *Hernia*. 2014;18(4):495-500. doi:10.1007/s10029-013-1113-8

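### The only caregiver-work item is Yes/No with no employment filter, so it cannot give the number of parental days off work and mixes households with no working caregiver with those that needed no leave

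*Combined protocol and SAP*

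**What the plan says.** The Objectives section lists two secondary outcomes. The second is "the impact of restriction type on number of parental days off work". The Summary says that "caregivers will complete a survey to assess time to resume full activity, time to return to school and work", and Data Collection repeats that "The survey includes assessments of the time taken to return to school and work, return to full activity, surgical complications".

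In Figure 2, the only item on caregiver work is "Did you or another caregiver take time off work to care for your child following their procedure", with Yes and No boxes. It is put to every family. It asks for no number of days and no return-to-work date, and offers no not-applicable option. The nearest household item is "What is your relationship to the child", which does not ask about employment. Data Collection states: "Baseline characteristics, comorbidities, surgical complications, length of stay, and pain medications will be obtained for each participant from the time of surgery". Employment is not named there, although baseline characteristics are not itemised.

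On allocation, the Participants section says: "Parents and patients who elected to participate then chose to enroll in the control group (PDAR) or experimental group (SDAR". Statistical Analysis provides only unadjusted two-group tests (t or Mann-Whitney, Chi-square or Fisher) at P<.05.

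**The concern.** The outcome is a count of days and the instrument records a yes or a no. That alone means the outcome cannot be computed from the survey as shown. Two further losses come with the Yes/No form.

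- **Ceiling.** If most working caregivers take at least one day off during ordinary recovery, both arms approach 100% Yes among working households, however much the number of days differs.
- **Structural zeros.** A household in which no caregiver works can truthfully answer only No, or leave the item blank. Its No looks the same as that of a working household that needed no leave, although restriction type could not have changed it.

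With equal employment in the two arms, the structural zeros weaken a real contrast. With unequal employment, which is possible because families choose their arm, they can create a contrast where none exists. If employment is not recorded, this can be neither seen nor adjusted for.

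**Working it through.** The documents state no sample size, effect size, employment rate or leave rate, so there is no planned figure to reproduce. **Every rate and arm size below is an assumption**. The Yes/No calculations show what the item would do if it were analysed as collected.

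**Model.** Let w be the share of households with at least one working caregiver and q the chance of any time off in such a household. If every other household answers No, P(Yes) = w × q.

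**1. Dilution, same w in both arms.** The observed difference is w × (q1 − q2). Power uses the arcsine approximation, two-sided .05: h = 2·arcsin√p1 − 2·arcsin√p2, and power = Φ(h·√(n/2) − 1.96). Take q = 0.90 vs 0.70 and 60 families per arm. If all households work, h = 0.516 and power is 81%.

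| w | Observed Yes | Difference | Power, all families (60 per arm) | Power, working households only (n per arm) |
|---|---|---|---|---|
| 0.95 | 85.5% vs 66.5% | 19 points | 70% | 79% (57) |
| 0.90 | 81% vs 63% | 18 points | 60% | 76% (54) |
| 0.85 | 76.5% vs 59.5% | 17 points | 52% | 74% (51) |
| 0.70 | 63% vs 49% | 14 points | 34% | 66% (42) |

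At w = 0.70, part of the fall from 81% to 34% is simply fewer informative families (81% to 66%). The part due to counting non-working households as No is 66% to 34%.

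**2. Spurious difference, no true effect, w differs by arm.** The false difference is q × (w1 − w2). With q = 0.95:
- 60% vs 80% working: 0.95 × 0.60 = 57% and 0.95 × 0.80 = 76%, a gap of 19 points. At 60 per arm the chance of P<.05 is about 60%.
- 80% vs 90% working: 0.95 × 0.80 = 76% and 0.95 × 0.90 = 85.5%, a gap of 9.5 points. The chance of P<.05 is about 26%.

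**3. Ceiling.** Suppose every working caregiver takes at least one day, with means of 5 and 3 days and SD 3. The Yes/No difference among working households is zero. On days, n per arm for 80% power is 2 × [3 × (1.960 + 0.842) / 2]² = 35.3, so 36.

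**4. Who gives the No answers?** With q = 0.90 vs 0.70 and equal arms, the non-working share of pooled No answers is 2(1 − w) / [(1 − 0.9w) + (1 − 0.7w)].
- w = 0.70: 0.60 / 0.88 = 68%
- w = 0.85: 0.30 / 0.64 = 47%
- w = 0.95: 0.10 / 0.48 = 21%

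**The case against.** The strongest reply is that the effect on the comparison rests wholly on assumed rates and may be modest. Much of that stands.

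- A reader might infer that the item measures employment rather than restriction type. The documents do not support this. They give no employment or leave rates, and step 4 shows that non-working households may supply well under half of the No answers. With equal employment the effect is dilution only. Bias needs an imbalance between arms, which is possible but not shown.
- A reader might infer that any household with an at-home caregiver must answer No. The item covers the respondent or another caregiver, so a household with one at-home and one working caregiver can truthfully answer Yes. Structural zeros arise only where no caregiver works, so w may be high and the loss small.
- A reader might infer that recovery days common to both arms distort the comparison. In a difference in mean days they cancel. They do harm only through the ceiling of the Yes/No form, which a day count largely removes.
- Nothing in Statistical Analysis says that a skipped item counts as no time off. A blank would be missing.
- Confounding from family choice affects every between-arm comparison here. What is specific to this item is that employment decides whether the outcome can occur at all.
- The sponsor could meet the employment part by showing that it is recorded among the baseline characteristics.

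None of this answers the missing day count, which is plain on the face of the survey. Nor does a day count by itself remove the structural zeros: the difference in mean days over all families would still be w times the difference among working households.

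The childcare item ("Did you have to find additional childcare for your child following their procedure") is also Yes/No, but childcare is not a named outcome and the point is not extended to it.

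**Conclusion.** The point holds in this form. As written, the plan cannot deliver the number of parental days off work, or a time to return to work, from the survey it shows. This part needs no assumption.

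The Yes/No item also mixes households with no working caregiver with working households that took no leave. How much that matters depends on unknown rates. Under 90% vs 70% and 60 per arm, all-family power is 34% to 70% for 70% to 95% working, against 66% to 79% when only working households are compared. An employment imbalance between the self-chosen arms could produce a false difference of about 9.5 to 19 points in the two cases shown. The documents do not establish that such an imbalance exists.

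One of two named secondary outcomes is affected. The primary outcome and the tracking of complications are not. The change should be made, but it is not critical to the trial.

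**What to change.** The protocol says enrollment is still accruing. For families still to be surveyed:

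1. Add before the work item: 'Was any caregiver of this child in paid work in the week before surgery? Yes/No'.
2. Replace the Yes/No item with the total number of work days missed by caregivers to care for the child after the procedure, with 0 allowed, optionally split into week 1 and later. Do not ask families to give a reason for the days. They know their arm and its instructions, so an attributed reason recalled at 4-6 weeks would be tied to the arm.
3. Compare days between arms among households with a working caregiver, using the t or Mann-Whitney test already planned.
4. Report the share of working households by arm.

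**Cost.** One added and one reworded REDCap item, with what should be a minor IRB amendment. Fewer families enter the work comparison, and families already surveyed lack both items, so their Yes/No answers can only be described separately. The filter still keeps households where an at-home caregiver made leave unnecessary. Other confounding from self-chosen arms remains.

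### The secondary outcome on parental days off work has no day count behind it: the only caregiver-work item in the printed survey is Yes/No

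*Combined protocol and SAP*

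**What the plan says.** The Objectives section lists "the impact of restriction type on number of parental days off work" among the secondary outcomes. Two other places describe the survey as measuring time away from work. The Summary says that "caregivers will complete a survey to assess time to resume full activity, time to return to school and work", and Data Collection says "The survey includes assessments of the time taken to return to school and work". Background and Significance gives part of the reason for the interest: "these restrictions create a societal burden through school absences and missed work days". Its closing paragraph also lists a description of parents' time off work among the aims.

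The survey is printed as Figure 2. Its one item on caregiver work reads "Did you or another caregiver take time off work to care for your child following their procedure", with tick boxes for Yes and No. The next row is a separate Yes/No question about extra childcare. The caption presents Figure 2 as the form in use: "Patients were able to complete the survey at their postoperative visit or online via REDCap".

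Under Statistical Analysis, continuous data are to be compared by t test or Mann-Whitney test, and categorical data by Chi Square or Fisher's exact test.

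**The concern.** The outcome is a count of days, but the printed item records only whether any time was taken. If the form in use matches Figure 2, the plan names an outcome that its own data cannot supply. The t test or Mann-Whitney test that would apply to it has no day values to work on.

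A Yes/No comparison does not stand in for the missing count. It asks whether restriction type changes the chance of missing any work, not how much work is missed. Many caregivers may take some time off after a child's operation whatever the instructions, and a difference between the arms could then lie mainly in the number of days. Lost work is part of the study's stated rationale, so this is a question the trial would be expected to answer.

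There is also a mismatch over whose time counts. The Objectives refer to parents. The survey item covers the respondent or another caregiver, and the item "What is your relationship to the child" allows grandparent, legal guardian and other as answers.

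**Working it through.** The documents state no figure for this outcome, so there is nothing to reproduce. The check traces the outcome to the fields that could supply it.

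1. **Items in Figure 2.** The section on the child has 12 rows and the section on the caregiver has 7, so 12 + 7 = 19.

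2. **Items that carry a duration or a date.**
   - Open day counts: 2, the child's return to school or daycare and the child's return to full activity.
   - Day bands: 1, the child's pain medication.
   - Open timing field: 1, when wound oozing occurred.
   - Days of work missed by a caregiver: 0.

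3. **Conditional follow-ups.** Four rows depend on the answer to an earlier item: two on wound oozing, one on complications and one on pain. None follows the work item in the text as read.

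4. **Other data source.** Data Collection lists baseline characteristics, comorbidities, surgical complications, length of stay and pain medications from the time of surgery. None of these records caregiver work.

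5. **What the Yes/No item yields.** No can be coded as 0 days. Yes means an unknown number above 0.
   - The mean in each arm, and the difference between means, cannot be computed.
   - The median is known only if more than half of an arm answers No, in which case it is 0.
   - A Mann-Whitney test with every Yes tied at one value would only compare proportions.
   - The proportion with any time off can be compared by Chi Square or Fisher's exact test.

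6. **Time to return to work.** The Summary and Data Collection speak of time until return to work, which is not the same quantity as days missed. The printed form gives neither.

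7. **Illustration, on assumed inputs only.** The documents give no proportion with time off and no day counts. Suppose the same share p answers Yes in both arms, and a Yes means 2 days on average in one arm and 4 in the other. The difference in mean days is p × (4 − 2):
   - p = 0.3 gives 0.6 days
   - p = 0.5 gives 1.0 day
   - p = 0.7 gives 1.4 days

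   In all three cases the printed item shows no difference.

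8. **Precision if a day field is added part-way.** If a share f of families in each arm supplies day counts, the standard error of the difference is about 1/√f times that with all families. For assumed f of 0.75, 0.50 and 0.25 this is 1.15, 1.41 and 2.0. The documents give neither the sample size nor the number already surveyed, so the true f is unknown.

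**The case against.** The strongest reply is that the printed form may not be the whole form. The live REDCap survey is not in the documents and may hold a day field. The text was also extracted from a PDF in which open fields appear as empty cells, and one follow-up on oozing shows no response options at all. A blank beside the Yes box could have been lost in the same way. This stands as a possibility, and it is why checking comes first. It is not the likelier explanation: the other follow-up rows were preserved, the work item runs straight into the childcare item, and the caption presents Figure 2 as the survey completed at the visit or online.

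A second reply is that Background and Significance sets only a descriptive aim for parents' time off work, which a Yes/No item can partly meet. That is fair, and it makes restating the outcome a legitimate repair. It does not reconcile the Objectives, which specify a number of days and an effect of restriction type.

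A reader might go further and infer that day counts would be biased because families with no employed caregiver would be coded as 0. The documents do not support this. Such a family does lose 0 work days, and the plan does not limit the outcome to employed caregivers. What remains is narrower. Under the Summary, "Participating families will choose to enroll in either the control (PDAR) or experimental (SDAR) groups", so the employment mix may differ between the arms. Employment is only one of the factors that self-selection could unbalance.

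**Conclusion.** The point holds as a mismatch between a named outcome and the printed data form. On Figure 2 as read, 0 of 19 items give the days missed by a family that answers Yes, and no other listed source fills the gap. One secondary outcome cannot be computed as worded. It should be fixed, and if accrual continues, each survey completed without a day field adds to the loss.

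The conclusion rests on the text as read and on Figure 2 being the form in use. A reader might infer that day counts were certainly never collected; without the live form, the documents do not establish that. Nor does the problem reach the main result. The primary outcome has its own day-count item, and preference is read from the choice of arm. The differences of 0.6 to 1.4 days in the working show what a Yes/No item can miss; they are not estimates for this trial.

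**What to change.** Check the source PDF and the live REDCap form. If a day field exists, show it in Figure 2.

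If it does not, and enrollment is still accruing as the Participants section states:

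- Keep the existing Yes/No item exactly as it is, so that families surveyed before and after the change remain comparable. Narrowing it to parents would break that.
- Add a follow-up for those who answer Yes, asking how many work days were missed. It should state whose days count (parents or any caregiver) and whether days are summed across caregivers. The Objectives should use the same definition.
- Code No as 0 and compare days by the planned Mann-Whitney or t test among families surveyed after the change. Report any time off for all families.
- Optionally, add a separate item on caregiver employment for description or a sensitivity analysis. It would not remove self-selection. A third answer on the Yes/No item would not serve, because it has no clear meaning when one caregiver works and another does not.

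If no field is added, or accrual has ended, restate the outcome as any caregiver time off work (yes/no) and correct the Summary, Data Collection and Objectives to match.

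Adding the field costs one or two short survey items and an amendment, and the day counts will cover later families only. The Background says that preliminary results are being reported, so some families have presumably been surveyed already. Re-contacting them would mean longer recall. Restating the outcome costs only wording but gives up the question of how many days are lost.

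### Families choose their arm, but time to full activity is compared with unadjusted tests and no analysis by procedure, so the primary comparison may be confounded

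*Combined protocol and SAP*

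**What the plan says.** The Summary (Study Design) sets allocation by preference: "Participating families will choose to enroll in either the control (PDAR) or experimental (SDAR) groups". The Participants section repeats this, and nothing in the documents mentions randomisation or any device to balance the arms.

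The Participants section admits two kinds of patient: "routine inguinal hernia repair (ages 2-13 years) or laparoscopic appendectomy for uncomplicated appendicitis (ages 0-17 years) were eligible for participation". Both arms are open to both procedures.

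The aim is comparative. The Summary (Background) says "We aim to compare time to full activity and post-operative outcomes", and the Objectives section adds "The primary outcome of this study is length of time to full activity".

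Under Statistical Analysis, continuous outcomes are to be "analyzed using unpaired t tests or Mann Whitney ranked sum tests", and categorical outcomes go to chi-square or Fisher tests, with significance at P below .05. That is all the inferential method the plan gives. The Data Collection section says "Baseline characteristics, comorbidities, surgical complications, length of stay, and pain medications will be obtained for each participant from the time of surgery", but no outcome analysis uses these data for adjustment.

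**The concern.** An unadjusted two-sample test estimates the effect of restriction type only if the arms are comparable in everything else that affects recovery. Randomisation would make that true on average. Family choice does not.

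Procedure, age and comorbidity could each plausibly affect both which arm a family picks and how soon the child is fully active. Procedure and age are also linked by eligibility: a child aged 0–1 or 14–17 can only be an appendectomy case. If the appendectomy share differs between the arms, age may differ with it.

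At stake is the meaning of the primary result. A difference in case mix could pass for a difference between SDAR and PDAR, or could mask one, and the nominal 5% error rate is not assured. The same applies to satisfaction, and to time off work, where the Objectives section speaks of the impact of restriction type.

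**Working it through.** **No plan figure to reproduce.** The documents state no sample size, SD, expected difference, choice rates or procedure mix. The tests and the 0.05 level come from the Statistical Analysis section. Every other input below is an assumption, and the test is taken as two-sided.

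**Bias from one factor.** Let X be a baseline factor (procedure, for example) that shifts mean time to full activity by d SDs, with no true arm effect. The unadjusted difference then estimates

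bias = d × [P(X | SDAR) − P(X | PDAR)].

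With X present in half the children:

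- *Mild case:* SDAR chosen by 65% of those with X and 45% of those without, d = 0.5.
  - P(X | SDAR) = 0.65/(0.65 + 0.45) = 0.591
  - P(X | PDAR) = 0.35/(0.35 + 0.55) = 0.389
  - Bias = 0.5 × 0.202 = **0.10 SD**
- *Strong case:* 70% versus 40%, d = 0.8.
  - P(X | SDAR) = 0.70/1.10 = 0.636
  - P(X | PDAR) = 0.30/0.90 = 0.333
  - Bias = 0.8 × 0.303 = **0.24 SD**

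With X at 30% or 70% prevalence instead, the biases are 0.084–0.087 and 0.202–0.212 SD.

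**False positives.** Simulation with 6,000 trials per setting, normal outcome, no true arm effect; N is the total in both arms:

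| Setting | Mann-Whitney, N=100 | Mann-Whitney, N=200 |
|---|---|---|
| Choice unrelated to X | about 5% | about 5% |
| Mild (65/45, 0.5 SD) | 7.6% | 10.2% |
| Strong (70/40, 0.8 SD) | 19.4% | 35.5% |

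In the mild and strong settings, a linear model with arm and X rejects 4.5–5.1% of the time.

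**The same mechanism in days.** Assume a within-procedure SD of 5 days and a difference of D days between procedures. Bias = D × (difference between arms in appendectomy share).

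- Shares 60%/40%: 0.4 days (D = 2) or 0.8 days (D = 4). The t test rejects 7–9% or 11–18% of the time.
- Shares 70%/30%: 0.8 or 1.6 days. It rejects 12–19% or 33–56%.

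The lower value in each range is 50 per arm and the higher is 100 per arm. Mann-Whitney rates are nearly the same, and adjusting for procedure gives about 5% throughout.

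To check the largest value: the SD in each arm is √(25 + 16 × 0.21) = 5.33 days, so the standard error with 100 per arm is 5.33 × √(2/100) = 0.753. Then 1.6/0.753 = 2.12, and the chance of exceeding 1.96 is about 56%. The bias stays fixed while the standard error shrinks, so more accrual raises the false-positive rate.

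**What adjustment leaves behind.** Add an unmeasured factor as strong as X and adjust for X only:

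| Setting | Bias (SD), unadjusted → adjusted | Rejection, N=100 | Rejection, N=200 |
|---|---|---|---|
| Mild | 0.20 → 0.10 | 15.0% → 8.1% | 25.5% → 10.1% |
| Strong | 0.49 → 0.27 | 54.3% → 21.5% | 84.5% → 37.8% |

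**The case against.** Several points can fairly be made for the plan.

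- **Pooling is not stated.** The analysis section does not say whether tests run overall or within procedure. This is true. However, the Background describes a single SDAR-versus-PDAR comparison across both procedures, and no by-procedure analysis is named, so pooling is the plain reading. Separate tests would still leave family choice confounding each one.
- **The age ranges prove little.** The hernia range lies wholly inside the appendectomy range, and nothing in the documents ties age or procedure to choice of arm. This stands: the age–procedure link does not itself create confounding by arm. Self-selection carries the argument.
- **Comorbidity may be restricted.** The eligibility figure is not available in the text reviewed, so its scope for confounding is unknown.
- **The percentages are assumed.** This stands. They show the mechanism and do not measure it in this trial.
- **The simulated null fits imperfectly.** PDAR carries a two-week restriction, so part of any difference in the primary outcome is built into the arms. Bias in the estimated difference therefore matters more than the false-positive rate. That bias is present whether or not the null is true.
- **Adjustment is only partial.** This also stands. Preference is the likeliest unmeasured factor, and the last table shows what would remain. It is a reason to word conclusions cautiously, not to leave measured imbalance uncorrected.

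**Conclusion.** The concern holds. Arm is self-selected, the aim is comparative, and the only tests specified take no account of baseline differences. Followed as written, the plan lets any imbalance in case mix pass straight into the primary comparison.

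Size and direction cannot be determined from the documents. Under the assumptions shown, the bias from one measured factor is about 0.10 to 0.24 SD, with false-positive rates of about 8–10% (mild) and 19–35% (strong) at N = 100–200. Adjustment restores about 5% only if that factor is the sole confounder and is well measured.

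This must be fixed because it concerns the primary comparison. That judgement rests on the design, not on any particular simulated rate.

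**What to change.** 1. **Name one primary estimator.** A suitable choice is linear regression of days to full activity on arm, procedure, age and comorbidity, with robust standard errors, reporting the adjusted difference in days and its 95% confidence interval. Propensity-score weighting is an acceptable alternative, but the SAP should commit to one and keep the other as a sensitivity analysis. Check that the sample supports the covariates. Add sex, site or surgeon only if recorded and if numbers allow.
2. **Show the arm difference within each procedure.**
3. **Give a baseline table by arm with standardised differences,** and keep the unadjusted tests as descriptive.
4. **Apply the same adjustment to satisfaction and time off work.** The Figure 2 survey asks "Did you or another caregiver take time off work to care for your child following their procedure" with a yes/no answer, so that model would be logistic unless a number of days is captured elsewhere.
5. **Word results as associations.** List unmeasured family preference and caregiver work situation as limitations, and note that the PDAR instruction itself builds in part of any difference.
6. **Date the change.** The Participants section says enrollment continues, while the Background refers to preliminary results. The amended SAP should state which results had been seen when the adjusted analysis was fixed.

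The cost is SAP wording and modest extra analysis. Procedure and age are needed for eligibility, and comorbidities are listed as collected. Sex and surgeon are not itemised, so their availability must be checked. Caregiver work situation is not a named variable or survey item, so adjustment cannot address it and residual confounding may be important.
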